11.7 Accrual rate, accrual duration, and study duration

11.7.1 Six institutions are expected to enroll patients onto this study: KCI, Henry Ford Hospital, University of Alabama at Birmingham, Ohio State University (OSU), Mount Sinai School of Medicine, and the Cancer Institute of New Jersey (CINJ). Their accrual rates are expected to be similar, at about 5-7 patients/year.

11.7.2 That yields a combined 6-institution expected accrual rate of 30-42 patients/year. At that expected accrual rate, it should take 27-37 months to enroll 92 patients (46 per treatment arm) among whom we should have at least 82 (41 per treatment arm) who are r-e for the primary endpoint.

11.7.3 Since a follow-up period of up to 7 months is required to determine the primary endpoint of the study, then the expected total study duration is 34-44 months.

12.0 ADVERSE EVENTS REPORTING

12.1 Regulatory and reporting requirements- These will be followed per IND requirements (if applicable) as well as sponsor requirements and WSU IRB requirements

12.2 Definition of Adverse Events (AE)

An adverse event (AE) is defined as any untoward medical occurrence in a subject administered a study drug and which does not necessarily have a causal relationship with this treatment. An AE can therefore be any unfavorable and unintended sign (including an abnormal laboratory finding), symptom, or disease temporally associated with the use of a study drug, whether or not related to the study **OR**

An abnormality identified during a medical test (e.g., laboratory parameter, vital sign, ECG data, physical exam) should be defined as an AE only if the abnormality meets one of the following criteria:

- induces clinical signs or symptoms.
- requires active intervention.
- requires interruption or discontinuation of study medication.
- the abnormality or investigational value is clinically significant in the opinion of the investigator.

12.3 WSU IRB Adverse Event Reporting Guidelines

Unexpected Problem – Risk to participant or others. A problem that is a) unforeseen b) indicates that participants or others are at increased risk of harm, and c) is related or possibly related to the research. The following are examples of unexpected problems:

1. **Adverse Event:** Any harm experienced by a participant regardless of whether the event was internal (on-site) or external (off-site) and regardless of whether the event meets the FDA definition of “serious adverse event”, which in the opinion of the principal investigator are both **unexpected, related (definitely, probably, or more likely than not), and suggests that participants are at greater risk than was previously known or recognized.**
 - a. An adverse event is “unexpected” when its specificity and severity are not accurately reflected in the informed consent document, the protocol or the investigator’s brochure.
 - b. An adverse event is “related to the research procedures” if in the opinion of the principal investigator it was more likely than not to be caused by the research procedures, or if it is more likely than not that the event affects the rights and welfare of current participants.
2. **Any harm experienced by a participant or others** as a result of involvement in research activities (internal or external **excluding** adverse events).
3. Information that indicates a **change to the risks or potential benefits** of the research. For example:
 - a. An interim analysis or safety monitoring report indicates that frequency or magnitude of harm or benefit may be different than initially presented to the IRB.
 - b. A paper is published from another study that shows the risks or potential benefits to your research may be different than initially presented to the IRB.
 - c. Study put on hold by the PI, FDA, or the Sponsor for reasons that may include safety, toxicity and/or efficacy.
4. **A change in FDA labeling** or withdrawal from marketing of a drug, device, or biologic used in a research protocol.
5. **Change to the protocol** taken without prior IRB review to eliminate an apparent immediate hazard to a research participant.
6. **Research conducted without prior WSU IRB approval.**
7. **Event that requires prompt reporting to the sponsor.**
8. **Unanticipated adverse device effect:** Any serious adverse effect on health or safety, or any life-threatening problem or death caused by, or associated with, a

device if that effect, problem, or death was not previously identified in natured, severity, or degree of incidence in the investigational plan or application (including a supplementary plan or application), or any other unanticipated serious problem associated with a device that relates to the rights, safety, or welfare of subjects.

9. **Sponsor-imposed suspension for risk.**
10. **Complaint of a participant** when the complaint indicates unexpected risks or cannot be resolved by the research team.
11. **A breach of confidentiality.**
12. **Protocol violation/deviation** (meaning an accidental or unintentional change to the IRB-approved protocol) that harmed participants or others, that indicates participants or others may have been placed at increased risk of harm, or rights of research participants were violated. For example:
 - a. Failure to draw safety labs
 - b. Request for continuation submitted late to the IRB three years in a row
 - c. Wrong informed consent signed or failure to obtain informed consent
13. **Incarceration of a participant** in a protocol not approved to enroll prisoners.
14. **All deaths that have happened at WSU or one of its affiliates within 30 days of the last study intervention, and not related to progressive disease.**
15. **Any death, if the PI feels that it is significant** no matter when it occurs.

IRB Policy

Principal investigators must report any of the above to the IRB as soon as possible, **but in all cases within 5 working days.**

12.4 Definition of Serious Adverse Events (SAES)

An AE is considered “serious” if, in the view of either the investigator or sponsor, it results in any of the following outcomes:

- results in death,
- is life threatening (an ae is considered “life-threatening” if, in the view of either the investigator or sponsor, its occurrence places the subject at immediate risk of death. it does not include an AE that, had it occurred in a more severe form, might have caused death.),
- results in persistent or significant disability/incapacity or substantial disruption of the ability to conduct normal life functions,
- results in congenital anomaly, or birth defect,
- requires inpatient hospitalization or leads to prolongation of hospitalization (hospitalization for treatment/observation/examination caused by ae is to be considered as serious),
- other medically important events.

12.5 Serious Adverse Event Reporting (SAE)

The SAE reporting will begin at the time of registration until 30 days after the last dose of either Enzalutamide or Bicalutamide. Within 24 hours of awareness of a serious adverse event, whether or not related to the study drug, the investigator will complete and submit a Medwatch 3500a form, containing all required information (reference 21 CFR 312.32). The investigator will submit a copy of this Medwatch 3500a form to the coordinating institution (PI- [name]) and Astellas by either e-mail or fax, within the same timeframe. Reporting to Astellas is only required for SAEs occurring on patients randomized to Arm A.

The SAE documentation, including the Medwatch 3500A form and available source records should be emailed or faxed to:

Astellas pharma global development – United States

Email: [contact]

[contact]

The following minimum information is required:

- study number/IIT regulatory identifier
- subject number, sex and age
- the date of report
- a description of the SAE (event, seriousness of the event)
- causal relationship to the study drug. Follow-up information for the event should be sent within 7 days as necessary. Copy of above should also be sent to coordinating site (PI- [name]).

Study Coordination Center/Principal Investigator:

[name]..D.

Contact Information [name]
[name].

[contact] and [contact] E
mail: [contact]

Every institution should also report SAE to their respective IRB per institutional guidelines.

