Bio-specimens: Baseline tumor tissue biopsies (bone is preferable but other sites permitted if patient has no accessible bone metastases for biopsy) will be mandatory for study enrollment. Post treatment core biopsies of bone tumor tissues will be encouraged and obtained from the patients in both arms.

Biomarkers: CXCR4, ERG and key androgen biosynthesis enzymes (SRD5A2, CYP17, CYP3A4, AKR1C3 and HSD17b6) will be analyzed in bio specimens.

Background and rationale: CXCR4 and TMPRSS2-ERG fusion genes were shown to be differentially regulated in human tumor tissues in African American and Caucasian men. CXCR4 has been shown to be associated with aggressive disease and could possibly be the reason for racial disparity in outcomes noted in African American men. TMPRSS2-ERG fusions were reported to be significantly localized to prostate tumors in Caucasian men. CXCR4 expression has been shown to be a key molecular predictor of bone metastasis. TMPRSS2-ERG fusion status is not known in bone metastasis. Published data demonstrate that TMPRSS2-ERG fusions are early markers for prostate cancer, but their expression is sustained in advanced cancers suggesting that fusion activated ERG factor is still functional in tumor cells. Both CXCR4 and TMPRSS2-ERG are androgen responsive genes in prostate tumor cells. Androgen biosynthesis enzyme expression has been shown to be persistent in advanced patients, who undergo hormonal therapy. We will analyze the expression of key enzymes (SRD5A2, CYP17, CYP3A4, AKR1C3 and HSD17b6) contributing to intratumoral androgen biosynthesis and test if the levels of these enzymes has an impact on response to ADT in either of the therapeutic arms of the study. Pre and post tumor tissues in both arms of the study will be analyzed for marker expression.

3.0 DRUG INFORMATION:

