10. Willingness to swallow pills and no medical condition that would interfere with this.
11. Male patient and his female partner who is of childbearing potential must use 2 acceptable methods of birth control (one of which must include a condom as a barrier method of contraception) starting at screening and continuing throughout the study period and for 3 months after final study drug administration. Patients are also required to use a condom if having sex with a pregnant woman.
12. Patient should agree to a tumor tissue biopsy prior to protocol enrollment. Post therapy biopsy is optional.
13. Patients who are being treated with a GNRH antagonist should be willing to switch to a LHRH analogue after registration.
14. Patients must have one of the following a) Low volume disease (defined as no visceral metastases and < 4 bone metastases) or b) are not candidates for docetaxel based chemotherapy or 3) refused docetaxel chemotherapy

4.2 Patients must NOT meet any of the following exclusion criteria:

1. History of seizure or any condition that may predispose to seizure (e.g., prior cortical stroke, significant brain trauma) at any time in the past. Also, history of loss of consciousness or transient ischemic attack within 12 months of Day 1 visit;
2. Known or suspected brain metastasis or active leptomeningeal disease;
3. Severe concurrent disease, infection, or co-morbidity that, in the judgment of the Investigator, would make the patient inappropriate for enrollment;
4. Absolute neutrophil count < 1,000/ μ L, or platelet count < 50,000/ μ L, or hemoglobin < 8 /dL) at the Screening visit.
5. Total bilirubin, alanine aminotransferase (ALT) or aspartate aminotransferase (AST) > 2.5 times the upper limit of normal
6. Creatinine > 177 μ mol/L (2 mg/dL)
7. Clinically significant cardiovascular disease including:
 - Myocardial infarction within 6 months;
 - Uncontrolled angina within 3 months;
 - Congestive heart failure New York Heart Association (NYHA) class 3 or 4, or patients with history of congestive heart failure NYHA class 3 or 4 in the past, unless screening echocardiogram or multi-gated acquisition scan performed within 3 months results in a left ventricular ejection fraction that is \geq 45%;

---History of clinically significant ventricular arrhythmias (e.g., ventricular tachycardia, ventricular fibrillation, torsades de pointes);

---History of Mobitz II second degree or third degree heart block without a permanent pacemaker in place;

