8.11 Toxicity- Evaluable patients

All patients registered on the protocol and starting therapy will be considered toxicity evaluable. Toxicity will be graded per the CTCAE criteria 4.0.

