10.0 CORRELATIVE STUDIES

10.1 Bio-specimens: Pretreatment tumor tissue biopsies will be mandatory for study enrollment. If patient has accessible bone metastases then bone biopsy is required. If patient has no bone metastases amenable to biopsy then tumor tissue biopsy can be conducted from other sites. Post treatment core biopsies of tumor tissues will be encouraged and obtained from the patients in both arms. Archival primary prostate tissue slides/blocks submission is required. A minimum of 10 unstained slides or block should be sent to [name] (see address below in section 10.7). **An additional optional tumor tissue biopsy will be requested when patients are progressing on study medication.** This phase constitutes castrate resistant, where patients were progressing on androgen ablation and androgen receptor targeted therapies. Collection of metastatic biopsy from the patients at this phase will be offered as an option. Molecular studies and data on the clinical samples at this stage are limited and we have a unique opportunity to collect the patient tissues at this phase. Genomic testing and evaluation of tumor tissue will be done by Caris Inc. and additional analysis will be done in [name] lab. We are collecting tumor biopsy

specimens prior to treatment and collection of specimens at the CRPC phase will improve our ability to monitor the biomarker response and determine pathways of resistance. The tissue procurement, handling and shipping procedures will be the same for each biopsy.

10.2 Biomarkers: CXCR4, ERG and key androgen biosynthesis enzymes (SRD5A2, CYP17, CYP3A4, AKR1C3 and HSD17b6) will be analyzed for mRNA and protein expression in bio specimens. AR CAG repeats and androgen receptor variant expression will be determined in tumor tissues.

10.3 Background and rationale: Prostate cancer cells over express CXCR4 receptor which has been critically involved in disease progression [16]. We showed that CXCR4 expression regulates key signaling pathways contributing to invasion of tumor cells [17] and bone tumor growth [18]. TMPRSS2-ERG fusions are frequently expressed in PC patients where androgens regulate ERG factor expression in PC cells [19]. We and others found a link between ERG and CXCR4 expression in prostate cancer patient tissues [20, 21].

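### The SAE rules do not clearly cover serious harm from the mandatory pretreatment biopsy: reporting opens at registration, and the AE definition requires dosing

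*Combined protocol and SAP*

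**What the plan says.** **The biopsy.** Section 10.1 states "Pretreatment tumor tissue biopsies will be mandatory for study enrollment" and adds "If patient has accessible bone metastases then bone biopsy is required". The Section 2.0 background also makes it mandatory. Section 10.4 prefers five cores for metastatic sites. Inclusion criterion 12 reads "Patient should agree to a tumor tissue biopsy prior to protocol enrollment". The Section 7.0 calendar puts the biopsy in the pre-study column, while footnote 5 asks only that fresh tissue be taken before therapy. Sections 5.2 and 7.0 allow up to 7 days between registration and the start of treatment.

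**The safety rules.** Section 12.5 sets the window: "The SAE reporting will begin at the time of registration until 30 days after the last dose of either Enzalutamide or Bicalutamide". Inside it the duty is broad: "Within 24 hours of awareness of a serious adverse event, whether or not related to the study drug". Section 12.2 defines an adverse event as "any untoward medical occurrence in a subject administered a study drug", and Section 12.4 builds the SAE definition on that term. Among the minimum items for an SAE report, Section 12.5 asks for causality to the study drug only. Section 8.11 says "All patients registered on the protocol and starting therapy will be considered toxicity evaluable", and Section 11.6.2 restricts toxicity rates to that set.

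**The IRB rules.** Section 12.3 requires a report to the IRB within 5 working days of unexpected problems, including harm from research procedures or research activities. Its heading definition requires the problem to be unforeseen.

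**The concern.** The pretreatment biopsy is the one invasive procedure that the protocol makes compulsory, and it is done for the correlative studies. The SAE rules are built around drug exposure and registration, and the biopsy can come before both. A patient admitted with bleeding, infection or fracture after a pre-registration biopsy would generate no SAE form under Section 12.5. If he never started therapy, he would appear in no safety table.

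Under Section 14.4 the Data and Safety Monitoring Committee reviews filed SAE forms and study-specific reports. A run of biopsy complications at one of the six sites might therefore not reach it while the procedure stayed compulsory. The protocol itself treats invasive procedures as relevant to safety: Section 12.7 lists an increase in their number among the amendments that need IRB approval.

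**Working it through.** This is mainly a reading of the text, so the rules are set side by side according to when a biopsy complication becomes serious.

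| Timing of the serious event | SAE window (12.5) | AE, hence SAE, definition (12.2, 12.4) | Result |
|---|---|---|---|
| Before registration, or in a man who never registers | Closed | Not met, no study drug given | No 24-hour report; Section 12.3 applies only if the harm was unforeseen |
| After registration, before first dose (up to 7 days) | Open | Not met, no study drug given | The two sections contradict each other |
| After first dose, up to 30 days after last dose | Open | Met | Reportable, but the minimum report content does not ask about causality to a procedure |

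Which row applies depends on when the biopsy is done, and the documents do not settle that:

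- Section 10.1 and the pre-study column point to the first row.
- Footnote 5 permits the second row.
- Criterion 12 can mean that the biopsy itself, or only the patient's agreement to it, comes before enrollment.

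The SAE rules fail to give clear coverage in either of the first two rows.

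**Exposure.** Section 11.5.1 needs 41 evaluable patients per arm and allows for 10% not evaluable: 41 / (1 − 0.10) = 45.6, rounded up to 46 per arm, and 2 × 46 = 92. This reproduces the plan's figure. It is a ceiling on enrollment. Men biopsied but never registered come on top, and their number is not given.

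**Illustration only.** The documents give no serious complication rate r for the biopsy. For assumed values, the expected number of events among 92 patients is 92r, and the chance of at least one is 1 − (1 − r)^92:

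| Assumed r | Expected events | Chance of at least one |
|---|---|---|
| 0.5% | 0.46 | 37% |
| 1% | 0.92 | 60% |
| 3% | 2.76 | 94% |

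These figures count every serious biopsy event among 92 patients, whenever it occurs. If a fraction f becomes serious before registration, the expected number outside the window is 92 × r × f. Since f is unknown and at most 1, the table gives upper bounds for the enrolled patients at each assumed rate.

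**The case against.** **Section 12.3 already reaches procedural harm.** A reader might infer that biopsy harm escapes every safety definition in the protocol. It does not. Section 12.3 refers to research procedures and research activities, has no registration or dosing start point, and also lists certain deaths. This stands, with limits. The heading confines it to unforeseen problems, so a recognised biopsy complication may not qualify. The consent pages are not available, so which risks count as foreseen cannot be checked. The route leads to the IRB within 5 working days, not to the coordinating site within 24 hours, and it feeds no trial dataset.

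**The timing is not settled.** A reader might take it as fact that the biopsy precedes registration. That is the more natural reading, but footnote 5 and criterion 12 leave room for another. Section 10.6 has the study ID written on the sample at collection, which fits a patient already known to the study, although the documents do not say when IDs are issued. This objection stands, but it exchanges a gap for a contradiction.

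**Later biopsies are covered.** A reader might extend the point to the optional biopsies. Calendar footnote 5 places the post-treatment biopsy 28 to 42 days after registration, and Section 10.1 offers the other at progression on study medication. Both normally fall inside the SAE window in dosed patients, so only the causality item is relevant to them.

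**The toxicity-evaluable set is sound.** It serves the comparison of toxicity by arm. A pretreatment biopsy event cannot be an effect of the assigned drug, so leaving undosed patients out is appropriate.

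**Other routes exist.** Section 12.2 has a second limb, for abnormal test findings, that does not repeat the dosing condition, and the Section 14.1 meetings discuss participant safety. A biopsy event could surface through either. Neither opens the Section 12.5 window earlier or requires a report of procedural harm.

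**Conclusion.** The point holds in a limited form. For a biopsy done before registration, a serious complication that arises in that interval is outside the 24-hour SAE route, and only the IRB rules for unforeseen problems can reach it. For a biopsy between registration and first dose, Sections 12.5 and 12.2 give opposite answers. Once the patient is registered and dosed, SAE reporting applies, though without a required statement on procedural causality.

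The conclusion rests on the text and on no assumed rate. Exposure is up to 92 enrolled patients plus an unstated number biopsied but not registered. A reader might take the 37%, 60% and 94% figures as the chance of a missed event. The documents do not support that, because both the complication rate and the share arising before registration are unknown. The primary analysis and the toxicity comparison by arm are unaffected. This is a gap in safety capture that should be closed because closing it is cheap.

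**What to change.** 1. Reconcile criterion 12, calendar footnote 5, and Sections 10.1, 12.2 and 12.5, so that the protocol states once when the biopsy occurs relative to consent and registration.
2. In Section 12.5, start reporting of SAEs related to protocol-required procedures at signed consent. Keep reporting of all SAEs from registration, as now.
3. In Section 12.2, widen the population to subjects given a study drug or undergoing a procedure that the protocol requires. Section 12.4 then follows without change.
4. Add causality to a protocol procedure to the minimum content of the SAE report.
5. List biopsy-related serious events separately among all biopsied patients, including those never registered. Leave the Section 8.11 set unchanged for the comparison by arm.

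The cost is a few sentences in the protocol, a few more SAE forms and one short listing. Sites would also need to record who was biopsied but not registered. No visit or procedure is added.
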